14.2.4.1 Complete Response

Complete Response (CR) is defined as a best overall response (see Section 9.15 for the derivation) of CR according to RECIST v1.1, as assessed by the BIRC or the investigator, respectively.

Each participant will have a complete response status (0: 'no CR'; 1: 'CR') at 9 and 12-months post-randomization.

Participants will be counted as non-responders in the assessment of CR, who

- do not have any evaluable post-baseline assessment,
- receive a new anticancer treatment prior to reaching CR,
- only have non-measurable disease with a best overall response at non-CR/non-PD,
- progress, die or drop out for any reason prior to reaching CR.

The CR rate (CRR) is the proportion of participants with CR in the analysis set.

The same analyses and summary statistics as described for the OR in Section 14.2.4 will be performed. Additional subgroup analyses will be done by treatment arm for all subgroup levels defined in Section 8.2.1.

Time to CR as assessed by BIRC or investigator is calculated for all patients who have a CR by BIRC or investigator, respectively, at any point during the study.

Time to CR is calculated for each responder as the number of days from the Date of Randomization until the Date of First Response. No censoring will be applied for this endpoint: patients who do not respond at any time during the study will be excluded from the analysis.

Summary statistics and an empirical cumulative distribution function plot for time to CR will be provided by treatment arm.

14.2.5 **Duration of Response**

DoR is defined as the time (in months) from the first evidence of response (partial or complete, as assessed by the BIRC or the investigator, respectively according to RECIST v1.1) to the first occurrence of progression (radiological or clinical, as assessed by the BIRC or the investigator, respectively) or death due to any cause. DoR will only be computed for participants with objective response (as defined in Section 14.2.4).

$$DoR = (date \ of \ PD \ or \ death - first \ CR/PR \ date +1) / 30.4375$$

Censoring rules for the analysis of DoR will follow the same as those applied to PFS described in Table 9. The DoR rates will be estimated at 6, 12 and 24 months post first evidence of response. DoR will be analyzed by treatment arms but without any between-arm comparisons.

Table 13: Analyses for DoR

Analysis	Population	Censoring rules (Table 7)	Endpoint	Statistical methods
Main	ITT	Primary	DoR as assessed by the BIRC	KM estimates (as described in Section 14.1.1), incl. Kaplan-Meier curves
Sensitivity	ITT	Primary	DoR as assessed by the investigator	KM estimates (as described in Section 14.1.1), incl. Kaplan-Meier curves
Subgroups	ITT	Primary	DoR as assessed by the BIRC	same as EFS subgroup analysis (Section 14.1.4) only for subgroups defined in Section 8.2.1, and to be presented in a forest plot

The number and percentage of CR, PR, death due to any cause and disease progression (radiological or clinical) as assessed by the BIRC or the investigator respectively and censoring reasons will be presented by treatment arm.

The DoR time or censoring time and the reasons for censoring will be listed.

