No sensitivity/supportive analyses (except DoR by investigator assessment) will be performed for the secondary efficacy endpoint duration of response (DoR) due to the reason that the analysis of DoR is not based on the ITT and must be seen itself as a supportive analysis. For this reason, DoR will be analyzed by treatment arms but without any between-arm comparisons.

The list of timepoints for the analysis of the proportion of participants with enteral and parenteral feeding (Section 14.3.2 of this SAP) has been revised to match the schedule of assessments for nutritional status in the study protocol.

In case the difference between the ITT and safety sets is less than 5%, demographics and baseline characteristics will only be assessed and summarized by arm in the ITT set using summary tables and figures.

No changes to the planned analysis of the efficacy or safety endpoints are planned due to the impact of Coronavirus disease 2019 (COVID-19) outbreak. Sensitivity analyses may be considered depending on the observed COVID-19 findings.

Additional outputs (summary table and listing) will be generated for a description of the impact by COVID-19 on the study. The number and percentage of participants will be presented for the following findings due to COVID-19:

- Adverse Events (MedDRA SMQ "COVID-19")
- Important protocol deviations
- Missed Visits (including number of missed visits and detailed reason)
- Missed efficacy evaluations (including number of missed efficacy evaluations)
- Drug administration missed doses

Xevinapant TrilynX Debio 1143-SCCHN-301/ MS202359 0006

- Drug administration dose adjustments
- Treatment discontinuation
- Study discontinuation
- Death

A frequency table will be produced for the SAF analysis set to present the number of participants with important protocol deviations related to COVID-19 (categorized by frequency of participants with an important protocol deviation overall as well as by category of protocol deviation and type of protocol deviation).

In addition, important COVID-19 protocol deviations will also be listed.

Outputs related to disposition and exposure will be amended to present reason of treatment/study discontinuations due to COVID-19 and treatment changes due to COVID-19 (if possible).

8 Analysis Sets and Subgroups

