8.1 Definition of Analysis Sets

The following analysis sets will be used for the planned analysis of the global study population: the screened set, the intent-to-treat (ITT) set, and the safety (SAF) set.

Screened Set

The Screened set will include all participants having signed the Informed Consent Form (ICF). Unless otherwise specified, this set will be used for disposition (summary and eligibility participant data for the Consort disposition diagram).

Intent-to-Treat Set

The ITT set includes all randomized participants. Participants will be analyzed according to the randomized treatment (assigned arm) assignment following the intention-to-treat principle. The ITT set will be the primary set for all summaries and analyses of efficacy.

Safety Set

The SAF set includes all participants who received any dose of any of the study intervention (xevinapant/matched placebo, cisplatin/carboplatin, IMRT). Any participants who are randomized to the placebo + CRT group but who are incorrectly administered any dose of xevinapant will be analyzed in the xevinapant + CRT group. Any participant randomized to the xevinapant + CRT who incorrectly receives only placebo rather than xevinapant will be analyzed in the placebo group. The SAF set will be used for all safety analyses and baseline characteristics.

Pharmacokinetic Set

The PK set will include all the participants who have undergone at least one PK sample scheduled. The PK set will be used for all PK analyses.

Analyses	Analysis Set			
	Screened Set	ITT Set	SAF Set	PK Set
Participant Disposition	✓			
Demographics and Baseline Characteristics		✓		
Medical/Surgical History		✓		
Prior Medications		✓		
Concomitant/Subsequent Medications		✓		
Surgical Procedures		✓		
Concomitant 5-HT3 receptor antagonist medication		✓		
Compliance and Exposure			✓	
Efficacy: Primary Endpoint		✓		
Efficacy: Secondary Endpoints		✓		
Safety and Tolerability			✓	
Health-Related Quality of Life		✓		
Health Resource Utilization		✓		
Pharmacokinetics (PK)				✓

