14.1.4 Subgroup Analyses of the Primary Efficacy Endpoint EFS

Subgroup analyses for the EFS as assessed by the BIRC and EFS as assessed by investigator (with primary censoring rule as defined in Table 4) will be performed by treatment arm for all subgroup levels defined in Sections 8.2.1 and 8.2.2. In the case of a low number of participants within a category (<5% of the randomized population), the categories may be pooled. All subgroup analyses are exploratory and will be performed unstratified. No adjustment for multiplicity will be performed.

Cox regression models will be fitted for the EFS time as dependent variable and with subgroup type, the treatment arm, and with and without the treatment by subgroup type interaction as explanatory variables. The unstratified HR and its corresponding 95% CI will be computed per subgroup level. A p-value for the interaction test (Likelihood Ratio test) comparing models with

and without the interaction term will be provided together with the hazard ratios and corresponding 95% CI of the interaction model parameter.

The HR and its corresponding 95% CI, overall and for each subgroup level will be presented in a forest plot.

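### The SAP excludes between-arm comparison of duration of response, yet its subgroup plan produces treatment hazard ratios for that endpoint

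*SAP*

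**What the plan says.** Protocol Section 10.4.3.4 had DoR analyzed by the EFS methods, which compare the arms. SAP Section 7 changes this. It limits the sensitivity and supportive analyses of DoR to the investigator-assessed version, on the ground that "the analysis of DoR is not based on the ITT and must be seen itself as a supportive analysis", and for the same reason drops the comparison of arms. SAP Section 14.2.5 repeats the rule: "DoR will be analyzed by treatment arms but without any between-arm comparisons". It also restricts DoR to participants with an objective response.

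Table 13 in Section 14.2.5 has three rows. The Main and Sensitivity rows call for Kaplan-Meier estimates and curves only. The Subgroups row, for BIRC-assessed DoR, specifies "same as EFS subgroup analysis (Section 14.1.4) only for subgroups defined in Section 8.2.1, and to be presented in a forest plot".

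Section 14.1.4 fits Cox models containing treatment arm and the subgroup factor, with and without their interaction. It states that "The unstratified HR and its corresponding 95% CI will be computed per subgroup level", asks for a likelihood-ratio p-value for the interaction, and adds that "The HR and its corresponding 95% CI, overall and for each subgroup level will be presented in a forest plot".

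Section 8.2 lists BIRC-assessed DoR among the endpoints for subgroup analysis, and Section 8.2.1 applies the four stratification factors to every endpoint on that list. Protocol Section 10.4.8 also names DoR among the secondary endpoints whose treatment effect and 95% CI are to be estimated by subgroup.

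**The concern.** The exclusion in Section 14.2.5 is unqualified and makes no exception for subgroups. A hazard ratio of xevinapant against placebo within a subgroup is a between-arm comparison, so one part of the section forbids what another part requires. A programmer cannot satisfy both. If the matter is left until after unblinding, whether a DoR forest plot appears in the report becomes a choice made with the results in view.

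The comparison is also weak in itself. Response is observed after randomization and may be affected by treatment, so responders in the two arms need not be alike at baseline. Dividing them further by stratification factor gives smaller sets with the same defect. A forest plot of such hazard ratios, shown beside those for EFS, PFS and OS, would look like evidence of the same kind, and it is not.

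**Working it through.** No sample size, power or error-rate figure is involved. The check is a comparison of texts and a count of outputs.

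**Step 1: what the rule covers.** SAP 7 and 14.2.5 exclude every between-arm comparison of DoR. The reason given is the analysis set. By SAP 8.1, "The ITT set includes all randomized participants", whereas DoR exists only for those who reached CR or PR.

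**Step 2: what the Subgroups row requires.** It imports Section 14.1.4 in full and narrows only the list of subgroups, to those in 8.2.1. Section 14.1.4 is a treatment comparison by construction: a Cox model with arm as a term, a hazard ratio per level, an interaction test and a hazard-ratio forest plot. Nothing in the row replaces these with descriptive output.

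**Step 3: count of outputs.** Levels in SAP 8.2.1:

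| Factor | Levels |
|---|---|
| Region | 3 |
| Primary tumor site | 2 |
| Lymph node involvement | 3 |
| T size | 2 |
| Total | 3 + 2 + 3 + 2 = 10 |

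This gives up to 10 subgroup hazard ratios and up to 4 interaction p-values, one per factor. Section 14.1.4 also places an overall hazard ratio on the forest plot. For DoR, that is the comparison in all responders that 14.2.5 excludes, so the treatment hazard ratios number up to 10 + 1 = 11.

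These are maxima. Sections 8.2 and 14.1.4 provide for pooling categories below about 5% of the randomized population. With 700 randomized, that is about 0.05 × 700 = 35 participants. Pooling would reduce the number of levels, and a two-level factor pooled into one would lose its interaction test.

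**Step 4: is the row an isolated slip?** No. Section 8.2 lists DoR independently of Table 13. The Subgroups row carries the same method wording as the corresponding rows for PFS (Table 10) and LRC (Table 12), where comparing the arms is intended. The likely explanation is that the Section 7 change reached the Main and Sensitivity rows but not the Subgroups row or the 8.2 list.

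**Step 5: does another passage resolve it?** SAP Section 7 does not say whether the DoR subgroup treatment effects of protocol 10.4.8 are kept or dropped. No other section does either.

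**The case against.** The strongest reply is that the consequence is small and already contained. SAP 14.2 confines confirmatory secondary testing to OS, Section 6.3 makes the other secondary p-values exploratory, and Sections 8.2 and 14.1.4 label all subgroup analyses exploratory and unadjusted. The Subgroups row also follows protocol 10.4.8, so it can be defended as protocol-compliant.

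The point about consequence stands: no boundary, error rate or decision depends on this row. It does not remove the contradiction, because the exclusion applies to an analysis that the SAP already calls supportive, and so exploratory status cannot serve as an implied exception. The protocol point also stands in part. It explains where the row comes from, and it means that deleting the row is a departure that must be recorded.

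Several stronger readings are tempting, and the documents do not support them.

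- A reader might infer that the SAP calls the DoR comparison invalid. It says only that the analysis is not ITT-based and is supportive. That responders are not a randomized set is a fair inference from the definitions, but not the SAP's statement.
- A reader might infer a bias in a known direction. The documents give no response rates by arm and nothing on how durable any additional responses would be, so neither direction nor size can be stated.
- A reader might take the ITT entry in Table 13's population column to mean that non-responders enter the DoR analysis. Section 14.2.5 limits DoR to responders, so the label names the parent set and has no effect on the computation.

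**Conclusion.** The SAP contradicts itself on DoR. Sections 7 and 14.2.5 exclude between-arm comparison; Table 13's Subgroups row and the list in Section 8.2 bring it back. Followed literally, the plan yields an overall hazard ratio, up to ten subgroup hazard ratios and up to four interaction p-values among participants selected after randomization.

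The size of the problem is modest. It would be wrong to infer that type I error is inflated or that the EFS or OS conclusions are at risk, since DoR lies outside the testing hierarchy. What is at stake is internal consistency and the presence in the report of a comparison that randomization does not protect. The conclusion rests on reading the reference to Section 14.1.4 as importing that whole method, which is what the row says. The counts assume that no category is pooled.

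**What to change.** Choose one of two edits:

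1. Delete the Subgroups row from Table 13 and remove DoR from the endpoint list in Section 8.2.
2. Keep a subgroup presentation, but replace the row with Kaplan-Meier summaries by arm within subgroup, stating that no hazard ratio, interaction test or hazard-ratio forest plot will be produced. Adjust the DoR entry in 8.2 to match.

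In either case, add a sentence to SAP Section 7 recording that the DoR subgroup treatment effects named in protocol Section 10.4.8 will not be estimated, with the reason already given there for the main analysis.

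As a side note only, the population column of Table 13 would be clearer if it read ITT participants with objective response.

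The cost is a few lines of SAP text. Option 1 means fewer outputs, and option 2 replaces the hazard-ratio plot with descriptive summaries. Neither needs new data or any change to the confirmatory analyses. The edit should be made before unblinding.

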14.2.6 Proportion of Participants with Radical Salvage Surgery

The proportion of radical salvage surgery is defined as the proportion of participants with radical salvage surgery, excluding elective neck dissection (END) without anatomopathological (A-P) evidence of residual malignant cells.

Participants experiencing END without A-P evidence of residual malignant cells, will be considered as **not** having experienced a radical savage surgery for the computation of the proportion of participants with radical salvage surgery.

Summary statistics will be provided for the number and proportion of participants with radical salvage surgery experienced before 9, 12, 24, 36, 48, and 60-months post-randomization. In addition, the proportions will be compared between the two treatment arms by using a stratified logistic regression model as described for the OR in Section 14.2.4. The number of participants with and without radical salvage surgery will be summarized by treatment arm and presented along with the odds ratio and the corresponding 95% CI.

If the number of events permits, time to radical salvage surgery will be analyzed using the same methods as described for the primary analysis of EFS in Section 14.1.1.

[figure not shown]

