Qualitative variables will be summarized by frequency counts and percentages. Unless otherwise stated the calculation of proportions will be based on the number of participants of the analysis set of interest. Therefore, counts of missing observations will be included in the denominator and presented as a separate category.

Descriptive statistics by nominal visit or time point, e.g., for laboratory measurements, will include only data from scheduled visits. Unscheduled visits will be included in the derivation of baseline or worst on-treatment values.

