9.12 Imputation of Missing Data

Unless otherwise specified, all data will be evaluated as observed, and no imputation method for missing values will be used.

Missing statistics, e.g., when they cannot be calculated, should be presented as "nd". For example, if n=1, the measure of variability (standard deviation [SD]) cannot be computed and should be presented as "nd".

Imputation rules for missing efficacy data are described in Section 14.

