14.2.3 Locoregional Control

Locoregional Control (LRC) time is defined as the time (in months) from randomization to the first occurrence of progression at the site of the primary tumor or the locoregional lymph nodes, either according to RECIST v1.1 or based on clinical assessment (radiological or clinical, as assessed by the investigator or the BIRC, respectively).

LRC = (date of PD (primary tumor or locoregional) – randomization date +1) / 30.4375

Censoring rules for the primary and sensitivity analyses of LRC are described in Table 11 below. The last adequate tumor assessment is defined as the last tumor assessment result that is not "Not evaluable" or "Not assessed". If a participant is meeting a multiple censoring situation, the earliest censoring criterion will be applied.

Table 11: Censoring rules for LRC

Situation	Primary	Sensitivity #1	Sensitivity #2
No evaluable baseline or post-baseline assessment	C	Right censored at the date of randomization	Right censored at the date of randomization
PD after 2 or more consecutive missing or inadequate tumor assessments	Right censored at last adequate assessment before the consecutive missing/inadequate assessments	Right censored at last adequate assessment before the consecutive missing/inadequate assessments	Not applicable
Initiation of a new anticancer treatment for the disease under investigation before any documented progressive disease	Right censored at their last adequate assessment before the initiation of the new anticancer treatment	Not applicable	Not applicable
No locoregional failure	Right censored at the date of their last adequate assessment	Right censored at the date of their last adequate assessment	Right censored at the date of their last adequate assessment

Abbreviations: LRC: Locoregional control; PD: Progressive disease

The secondary endpoint analysis of LRC will consist of the analyses as presented in Table 12 below and will follow the same methods as described for EFS. The LRC rates will be estimated be at 9, 12, 18, 24, 36, 48 and 60 months post-randomization.

Table 12: Analyses for LRC

Analysis	Population	Censoring rules(Table 9)	Endpoint	Statistical methods
Main	ITT	Primary	LRC as assessed by the investigator	same as primary EFS analysis (Section 14.1.1), incl. Kaplan-Meier curves
Sensitivity	ITT	Primary	LRC as assessed by the BIRC	same as primary EFS analysis (Section 14.1.1), incl. Kaplan-Meier curves

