14.2.4 Objective Response

Objective Response (OR) is defined as a best overall response (see Section 9.15 for the derivation) of CR or PR according to RECIST v1.1, as assessed by the BIRC or the investigator, respectively.

Each participant will have an objective response status (0: 'no OR'; 1: 'OR') at 9 and 12-months post-randomization.

Participants will be counted as non-responders in the assessment of OR, who

- do not have any evaluable post-baseline assessment,
- receive a new anticancer treatment prior to reaching CR or PR,
- only have non-measurable disease with a best overall response at non-CR/non-PD,
- progress, die, or drop out for any reason prior to reaching CR or PR.

The OR rate (ORR) is the proportion of participants with OR in the analysis set.

OR status as assessed by BIRC will be compared between the two treatment arms by using a logistic regression model adjusted for randomization stratification factors. The same stratification factors used for the randomization will be applied to the analysis. The number of participants with

OR will be summarized by treatment arm and presented along with the odds ratio and the corresponding 95% CI.

The SAS code for the logistic regression model is specified in Appendix 6

A sensitivity analysis will be performed based on the OR as assessed by the investigator.

The number and percentage of participants with a best overall response of CR, PR, SD, non-CR/non-PD, PD, and NE as assessed by the BIRC or the investigator, respectively will be summarized by treatment arm.

The best overall response of CR, PR, SD, non-CR/non-PD, PD, and NE as assessed by the BIRC or the investigator, respectively, will also be listed together with the OR status.

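### Late milestone rates for radical salvage surgery, locoregional control and subsequent treatment are not the risks a reader will take them for; cumulative incidence with death competing is a cheap improvement

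*SAP*

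**What the plan says.** **Salvage surgery (SAP 14.2.6).** The plan reports "the number and proportion of participants with radical salvage surgery experienced before 9, 12, 24, 36, 48, and 60-months post-randomization" on the ITT set, with a logistic model, odds ratio and 95% CI. It adds that "The number of participants with and without radical salvage surgery will be summarized by treatment arm". The only classification rule given is that elective neck dissection without residual malignant cells counts as no surgery. A time-to-event version is conditional: "If the number of events permits, time to radical salvage surgery will be analyzed using the same methods" as for EFS.

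**General rules.** SAP Section 9 says "the calculation of proportions will be based on the number of participants of the analysis set of interest" and keeps missing observations in the denominator as their own category. SAP 9.12 says "all data will be evaluated as observed, and no imputation method for missing values will be used". Objective response has an explicit list in SAP 14.2.4, beginning "Participants will be counted as non-responders in the assessment of OR, who", and that list covers drop-outs. SAP 14.2.6 refers to 14.2.4 only for the model.

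**Locoregional control (LRC, SAP 14.2.3).** The event is locoregional progression only, and Table 11 has no row for death. A death without locoregional failure therefore falls under the no-failure row and is censored at the last adequate assessment. The primary rule also censors at new anticancer treatment: "Right censored at their last adequate assessment before the initiation of the new anticancer treatment". The plan states: "The LRC rates will be estimated be at 9, 12, 18, 24, 36, 48 and 60 months post-randomization".

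**Subsequent systemic treatment (SAP 14.2.7).** Anyone without such treatment is censored at last known contact, and rates are given to 60 months. No competing-risk estimate appears for either endpoint in the text available.

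**Status.** SAP 14.2 tests no formal hypothesis for any secondary endpoint except OS.

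**The concern.** A row labelled as surgery before 48 or 60 months will be read as a 4- or 5-year risk. If many participants have not been followed that long, a count over the full ITT set is lower than that risk, and it will rise at later cut-offs partly because follow-up lengthens. It is also undefined who enters the logistic model at a late milestone.

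The two Kaplan-Meier endpoints err in the other direction. Censoring deaths gives a net rate, which describes failure as if death without failure could not occur. In a population with high mortality, one minus that rate is above the share of participants who fail locally or receive later treatment.

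At stake are descriptive statements about local failure, salvage surgery and later therapy. A confidence interval shows sampling error but neither of these shifts.

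**Working it through.** **Design check.** The plan gives no numerical target for these three endpoints, so the calendar behind them was checked through the design. A group-sequential simulation with the Table 3 events and hazard ratios gives power of 88.2% for EFS with the first-interim futility bound applied (Table 3: 88.2%) and 79.7% for OS (Table 3: 79.6%). With 350 per arm, EFS medians of 17 and 23.3 months, 22-month recruitment and 5% yearly dropout (Protocol 5.5; hazard 0.00427/month), the EFS events at months 30/37/44 are:
- uniform accrual: 319/391/446
- linear ramp-up: 275/359/422
- Table 2: 279/365/429

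Ramp-up fits better. Both shapes are carried forward as assumptions.

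**Who can have reached a milestone.** The share with potential follow-up of m months at cut-off T is ((T-m)/22)^g, bounded between 0 and 1, with g = 1 (uniform) or 2 (ramp-up).
- Month 44, 24 months: 20/22 = 91%; squared, 83%
- Month 44, 36 months: 8/22 = 36%; squared, 13%
- Month 44, 48 and 60 months: 0%
- Month 65, 48 months: 17/22 = 77%; squared, 60%
- Month 65, 60 months: 5/22 = 23%; squared, 5%

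The 48- and 60-month zeros at month 44 do not depend on the accrual shape. The 60-month row would be complete, apart from dropout, only at month 22 + 60 = 82.

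**Salvage shortfall.** The documents give no salvage rate. Assume a true cumulative incidence F(m) = P(1 - exp(-m/tau)), with P = 12% and tau = 12 or 24 months. The observed proportion is the integral from 0 to m of F'(t) x share(t) x exp(-0.00427t). Example at month 44, m = 36:
- tau 12: true 11.40%, observed 10.63% (uniform) or 10.44% (ramp-up)
- tau 24: true 9.32%, observed 8.27% or 7.95%

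So the shortfall is 0.8-1.4 points. Setting dropout to zero isolates the cut-off:

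| Cut-off | Row (months) | Shortfall with 5%/yr dropout | Cut-off alone |
|---|---|---|---|
| Primary, month 44 | 36 | 0.8-1.4 | 0.3-1.0 |
| Primary, month 44 | 48 | 1.1-2.4 | 0.7-2.0 |
| Primary, month 44 | 60 | 1.2-3.0 | 0.8-2.6 |
| Final, month 65 | 48 | 0.55-0.75 | 0.01-0.08 |
| Final, month 65 | 60 | 0.6-1.2 | 0.1-0.5 |

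At month 44 the observed 48- and 60-month rows are identical (for example 10.68% in both, uniform, tau 12). With plateaus of 5-20%, the 36-month primary-analysis shortfall is 0.3-2.3 points. For scale, one per-arm standard error at 12% is sqrt(0.12 x 0.88/350) = 1.7 points. With plateaus of 8% against 12% and the same timing in both arms, the true odds ratio is 0.64 and the observed one 0.64-0.65.

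**LRC.** Take the phase 2 placebo figure of 56% at 36 months (Protocol 13.7), assumed to be a death-censored Kaplan-Meier estimate. Assume a hazard d of death without failure of 0.003-0.012/month. Front-loaded failure: H(t) = A(1 - exp(-t/tau)), tau 12 or 24, with A set so that exp(-H(36)) = 0.56. Constant hazard: -ln(0.56)/36 = 0.0161/month. Cumulative incidence is the integral of H'(s)exp(-H(s))exp(-ds).
- One minus Kaplan-Meier: 44.0%
- Cumulative incidence, front-loaded: 42.9% to 38.3%, excess 1.1-5.7 points
- Cumulative incidence, constant hazard: 41.9% to 36.5%, excess 2.1-7.5 points

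**Subsequent treatment.** There is no document figure. Assuming 20-40% net treated by 36 months and the same death hazards, the excess is 0.8-5.3 points with front-loaded treatment (tau 24) and 1.0-6.9 with a constant hazard.

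**The case against.** **The general rules may already cover it.** A reader might infer that the SAP counts everyone without a recorded operation as without surgery. The documents do not say so: Section 9 allows a separate missing category, and a participant not followed to the milestone could sit there. This stands as a limit on the claim. It does not rescue the rate, because the denominator is the full analysis set either way, and it leaves open who enters the logistic model.

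**The handling may be in material not shown.** Section 9 points to mock shells, and the logistic code in Appendix 6 is not visible. That is possible, but the rule belongs in the text of 14.2.6, as it does in 14.2.4.

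**The conditional analysis would probably run.** At a 12% plateau about 56-75 operations would be recorded by month 44 (700 x 7.98% to 10.68%), which may well be enough. At 5% it would be 23-31. No threshold is stated, and an analysis run with the EFS methods would by default also censor deaths.

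**Much of the shortfall is dropout.** This is correct. At month 65 it is most of it, so the effect should not be put down to the cut-off alone. Restricting the table to fully followed milestones would not cure dropout. It would also remove protocol-specified rows (Protocol 10.4.3.7) that carry almost no cut-off bias, such as 24 months at the primary analysis (0.01-0.03 points).

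**A death-censored LRC rate is conventional.** It matches the cause-specific log-rank and Cox analyses, and progression counts with censoring reasons are already planned. Those counts are not a cumulative incidence.

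**Conclusion.** The concern holds as a minor, inexpensive improvement to descriptive secondary rates. The late salvage rows are low as milestone risks. At the primary analysis the 48- and 60-month rows describe follow-up that nobody can yet have. The LRC and subsequent-treatment rates are net of death and read high as shares of participants.

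The direction follows from the definitions. The sizes rest on assumed plateaus, timing, accrual shapes and death hazards, and on reading the phase 2 LRC figure as death-censored. The 36-month salvage shortfall at the primary analysis, at a 12% plateau, is below one standard error; at 48 and 60 months it can exceed one.

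Two stronger readings are not supported. A reader might infer that the treatment comparison is distorted. The salvage odds ratio barely moves if surgery timing is alike in both arms, and log-rank and Cox remain valid as cause-specific comparisons. A reader might also infer that the LRC excess is larger in the arm with more failures. That depends on the hazards of death without failure: with tau 12 at 36 months, LRC of 56% with d = 0.003 gives 1.1 points, while LRC of 78% with d = 0.006 gives 1.2. EFS, PFS, OS and alpha are not affected.

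**What to change.** - **SAP 14.2.6:** make the time-to-event analysis of salvage surgery unconditional. Report its milestone rates by Aalen-Johansen cumulative incidence with death as the competing event. This handles both short follow-up and dropout, the latter under the usual non-informative censoring assumption.
- **Crude table:** keep the protocol-specified rows. State whether a participant not followed to the milestone is missing or without surgery, and show the number followed to each milestone. Mark rows that no participant has reached at the cut-off as not estimable (48 and 60 months at the EFS primary analysis on planned timing).
- **SAP 14.2.3 and 14.2.7:** add cumulative-incidence rates, with death competing, beside the planned Kaplan-Meier rates. For LRC use the Sensitivity #1 or #2 censoring, or state that the rate is still net of new anticancer treatment.
- **Comparisons:** keep log-rank and Cox, described as cause-specific.

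Cost: SAP wording, a standard PROC LIFETEST option (eventcode=), a little extra programming and one more definition to explain. Antineoplastic therapies, including surgery, are already recorded to end of study (Protocol 6.5). The primary analysis and alpha do not change.
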